- o. Blood samples for PK assessments will be collected on the first day of full target dose administration immediately prior to the VP-315 dose and at 2- and 5-minutes post first injection and 2-, 5-, 10-, 20-, 30-, 60-, and 120-minutes post last injection; samples will also be collected on the following day 24 hours (±1 hour) post prior injection of VP-315. Blood samples for PK assessments will only be collected for subjects in Part 2 (Cohorts 4 and 5 expansion groups).
- p. Photography of BCC lesion taken by a study team member prior to each treatment through EOS. Evaluation of lesion necrosis by the SRC (Part 1) or Medical Monitor (Part 2) is required for continued treatment.
- q. Subjects in Part 2, will complete SCAR-Q and FACE-Q if they feel they have scars related to study treatment (relevant subscales only) at Safety Assessment Visits, and EOT.
- r. Subjects will return approximately 7- or 14-days after excision (EOS) for a postsurgical assessment (7 days on the face and 14 days on the body). Subjects with excised lesions on both the face and the body will be required to complete 2 EOS visits accordingly.
- s. Subjects with AE(s) at the EOS visit will be contacted by phone at least 30 days after the EOS visit to confirm the status of any ongoing AE(s).
- t. Limited Safety Assessment Visit conducted only in Part 2
  - a. Cohorts 1-2: If the treated lesion is not fully necrosed at the W2D4 Safety Assessment Visit, a Limited Safety Assessment Visit should occur on W3D1 for further evaluation of the lesion for necrosis. No additional treatment will be adminstered.
  - b. Cohorts 4-5 (including expansion groups): If only 1 target lesion is treated and complete necrosis is not achieved at the W1 Safety Assessment Visit, subjects should return on W2D1 for further evaluation of the lesion for necrosis. No additional treatment will be administered. If a second target lesion was treated and complete necrosis is not achieved at the W2 Safety Assessment Visit, subjects should return on W3D1 for further evaluation of the lesion for necrosis. No additional treatment will be administered.
- u. Scar Cosmesis Assessment and Rating (SCAR) Scale will be completed by the site investigator prior to excision at the EOS Visit.

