## 8.5.3 Subject-reported Outcomes

In Part 2 of the study, subject-reported outcomes will be collected with the SCAR-Q (Scar appearance, Scar symptoms, and Psychosocial impact scales) (Appendix 3) and relevant subscales of the FACE-Q (Appendix 4) (Satisfaction with outcome) completed at each Safety Assessment Visit, and EOT visit.

The FACE-Q will only be completed by subjects who have target or nontarget lesions on the face.

Brief instructions are provided at the start of each scale, and questionnaires will be administered via electronic Patient Reported Outcomes tablets during the subject visit in accordance with Table 8-1.

Each SCAR-Q and FACE-Q scale provides 4 response options that measure frequency. All scales use a 4-point scale. There is no overall or total score, only scores for each independent scale. Each scale is transformed into scores that range from 0 to 100. The scores are computed from the responses to the items by adding them together and converting the raw score to a scale from 0 to 100. Higher scores reflect a better outcome.

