### **5.6. Handling Dropouts and Missing Data**

Unless described otherwise in other sections of this SAP, analyses will be carried out with the data available using no imputation for missing data.

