### 10.1. SCAR-Q – Appearance Scale

A summary of SCAR-Q – Appearance will be provided using the full analysis population. Descriptive statistics will be provided for Raw Sum (12 = Best to 48 = Worst), Rescored Sum (12 = Worst to 48 = Best), and Score (0 = Worst to 100 = Best). The number and percentage of subjects falling into each scale level (1 = Not at all, 2 = A little, 3 = Quite a bit, 4 = Very much) for responses to the following twelve “How much are you bothered by...” assessment questions will be provided in the summary:

1. How your scar looks from far away
2. How wide your scar looks
3. How your scar looks from different angles
4. How thick your scar looks (more raised than you would like)
5. The length of your scar
6. The surface of your scar (more bumpy than you would like)
7. The color of your scar
8. The difference between the color of your scar and your skin color
9. The contour of your scar (not as flat as you would like)
10. The overall size of your scar
11. How your scar looks close up
12. How noticeable your scar is

Raw Sum is calculated as follows:

- If the number of missing responses is 0, then Raw Sum is the total of the numeric response values.

- If the number of missing responses is  $>0$  and  $<6$ , then Raw Sum is  $[(\text{number of missing responses} \cdot \text{mean of non-missing response}) + \text{total of non-missing numeric response values}]$ .
- If the number of missing responses is  $\geq 6$ , then Raw Sum is missing.

Rescored Sum is calculated as follows:

- Each non-missing numeric response value is transformed into  $5 - \text{response value}$ .
- Then proceed the same as for Raw Sum, except use transformed response values.

Score is calculated as follows:

- If Rescored Sum is missing, then Score is missing.
- Otherwise, Score is provided by the SCAR-Q Conversion Table.

The summary will present Raw Sum, Rescored Sum, Score, and the above listed questions within scheduled visit (W1 Safety Assessment, W2 Safety Assessment, EOT).

A separate listing will be provided for SCAR-Q – Appearance using the full analysis population, and this listing will include Visit, Date of Visit, and the parameters as described above.

Only Part 2 will be summarized.

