### 10.3. Scar Assessment

A summary of the Scar Assessment will be provided using the full analysis population. The number and percentage of subjects falling into each response category for the following items will be provided in the summary:

- Subject Asked if Any Scars are Related to Study Treatment (Yes, No)
- Subject Response to Scars Inquiry (Yes, I have scar(s), No, I don't have any scar(s));

And for each scared lesion (TL1, TL2, NTL1, NTL2, NTL3):

Verrica Pharmaceuticals Inc.  
Protocol: VP-315-201

Statistical Analysis Plan  
6-Sep-2024

- Severity of Lesion Scar (Mild, Moderate, Severe)
- Lesion is Most Bothersome to Subject (Yes, No)

The summary will present the above listed parameters within scheduled visit (W1 Safety Assessment, W2 Safety Assessment, EOT).

A separate listing will be provided for the Scar Assessment using the full analysis population, and this listing will include Visit, Date of Visit, and the parameters as described above.

Only Part 2 will be summarized.

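### Under Table 8-1 footnote q the SCAR-Q mean covers only subjects who report a scar, is not labelled so, and can fall when there are fewer mild scars; the FACE-Q selection rule needs reconciling

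*Protocol*

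**What the plan says.** **Who completes the questionnaires.** Footnote q to Protocol Table 8-1 (Section 8.3) says that Part 2 subjects "will complete SCAR-Q and FACE-Q if they feel they have scars related to study treatment". Protocol 8.5.3 has both instruments "completed at each Safety Assessment Visit, and EOT visit" and mentions no scar condition; Protocol 8.2 is the same. The one restriction in 8.5.3 concerns lesion site: "The FACE-Q will only be completed by subjects who have target or nontarget lesions on the face". Section 8.5.3 also refers to Table 8-1 for the administration of the questionnaires. SAP Section 14, which lists departures from the protocol, does not mention the point.

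**How scores are summarised.** SAP 10.1 (SCAR-Q Appearance) and 10.2 (FACE-Q Psychological Function) give descriptive statistics of the score by visit in the full analysis population, for Part 2 only. On the direction of the scales, Protocol 8.5.3 says "Higher scores reflect a better outcome". For a SCAR-Q form without enough answers, "If Rescored Sum is missing, then Score is missing". The general rule in SAP 5.6 is that "analyses will be carried out with the data available using no imputation for missing data". No value is set for a subject without a scar.

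**What is reported about scars themselves.** In SAP 10.3, "A summary of the Scar Assessment will be provided using the full analysis population". It counts subjects who say they do and do not have a scar, at the same three visits (Week 1 and Week 2 Safety Assessments, and EOT). It is a separate table, and 10.1 and 10.2 do not refer to it.

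**The concern.** Whether a subject feels scarred is itself an outcome of treatment. If it decides who fills in SCAR-Q, the mean is taken over a group that treatment helped to select. A table described as using the full analysis population would be read as describing all analysed subjects when it describes only those with a scar.

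SAP 5.5 shows Cohorts 4 and 5 as separate groups, so a reader will naturally set the two-day and three-day regimens side by side. A regimen that spares more subjects a mild scar loses those subjects' high scores from its mean and may look worse for it.

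For FACE-Q the issue is different. The footnote and the text select different people: a subject with a facial lesion and no scar is left out by the footnote, while nothing in 8.5.3 leaves that subject out.

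**Working it through.** The documents give no expected score, scar rate or sample-size figure for these endpoints, so there is no stated figure to reproduce. The check asks whether the mean among completers can move the wrong way, and under what condition.

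**Inputs from the documents:** score range 0 to 100, higher better; Cohort 4, 36 subjects (SAP 3.6); Cohort 5, 37 subjects (SAP 3.7).

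**Assumed, for illustration only:** a mild scar scores 85, a worse scar 60, and the numbers with no scar are as shown. Where an all-subject mean is given as a yardstick, no scar counts as 100. Nobody is assumed missing for other reasons.

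**General condition.** Take n completers with mean M, of whom k, each scoring m, end up with no scar and so give no score. The new mean is (nM − km)/(n − k), which is below M exactly when m > M. Avoiding scars that score above the average lowers the mean.

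**One cohort of 36, with 18 mild and 18 worse scars.** Some mild scars become no scar, and no other subject changes.

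| Mild scars avoided | Mean among completers | All-subject mean (no scar = 100) |
|---|---|---|
| 0 | (18×85 + 18×60)/36 = 72.5 | 72.5 |
| 6 | (12×85 + 18×60)/30 = 70.0 | (600 + 2100)/36 = 75.0 |
| 12 | (6×85 + 18×60)/24 = 66.25 | (1200 + 1590)/36 = 77.5 |
| 18 | (18×60)/18 = 60.0 | (1800 + 1080)/36 = 80.0 |

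No subject is worse off in any row than in the row above, yet the reported mean falls by 12.5 points from first to last. The middle column needs no value for an unscarred subject.

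**Two regimens at the SAP's cohort sizes.**
- A (36): 18 no scar, 6 mild, 12 worse. Completers: (6×85 + 12×60)/18 = 68.3. All subjects: (1800 + 1230)/36 = 84.2.
- B (37): 4 no scar, 21 mild, 12 worse. Completers: (21×85 + 12×60)/33 = 75.9. All subjects: (400 + 2505)/37 = 78.5.

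A is 7.6 points worse among completers and 5.7 points better over all subjects. With the same counts, mild scores of 75, 85 or 95 and worse scores of 40 or 60, A is 4.5 to 16.7 points worse among completers and 1.5 to 9.7 points better over all subjects, in all six combinations.

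**The direction is not fixed.** If the 6 scars avoided in the cohort of 36 were worse scars instead, the completer mean would be (18×85 + 12×60)/30 = 75.0, up from 72.5. The distortion arises when the scars avoided are the milder ones.

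**FACE-Q.** This arithmetic does not carry over. The ten Psychological Function statements in SAP 10.2 concern general self-regard and mood, not scars, so nothing in the documents says where unscarred subjects would score.

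**The case against.** **The two protocol texts can be read together.** Section 8.5.3 points to Table 8-1, and its facial-lesion rule is worded as a necessary condition. On that reading footnote q adds a second condition. This partly stands. A reader might infer from footnote q alone that a subject with only a body scar would complete FACE-Q; the restriction in 8.5.3 rules that out. What remains is that 8.2 and 8.5.3 omit the scar condition, so sites could follow either rule for an unscarred subject with a facial lesion.

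**SCAR-Q presupposes a scar.** Protocol Appendix 3 describes it as an instrument for people with scars, and all twelve items ask about one. This stands: the condition is reasonable for SCAR-Q. The problem is that the mean is not labelled as conditional.

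**The selection is already visible.** SAP 10.3 gives scar responses in the same population at the same visits, and SAP 5.2 includes the number of subjects with every mean. The clinician-scored SCAR Scale in Cohorts 4 and 5 (SAP 10.4) has no scar condition, and its lowest scar-spread level covers no scar. A reader might infer that the plan cannot address its satisfaction objective at all; these summaries show otherwise. They are not tied to the SCAR-Q score, however.

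**Little rests on it.** The study is not randomised, nothing is tested, and the objectives tables class these endpoints as exploratory (Protocol 11.4.2 also lists them among efficacy endpoints). This stands and limits the importance of the point.

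**Conclusion.** The point holds, as a minor one. Under footnote q the SCAR-Q Appearance mean is conditional on reporting a scar and the SAP does not say so. The cohorts' SCAR-Q means should not be compared without the no-scar share beside them.

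The figures show that a reversal can happen, not that it will. The scores and scar counts are assumed, and the reversal needs the avoided scars to be the milder ones. The conclusion also assumes that sites applied footnote q. The scar question in SAP 10.3 fits that rule, but the documents do not confirm it.

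For FACE-Q the supported statement is narrower. Unscarred subjects with facial lesions are left out for a reason unrelated to what the analysed scale measures, and the direction of any bias is unknown. A reader might infer that the best FACE-Q outcomes are lost; the content of the scale gives no basis for that.

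**What to change.** 1. **FACE-Q rule.** Reconcile footnote q with Protocol 8.2 and 8.5.3 so that FACE-Q goes to every subject with a facial lesion, scar or not. The SAP is dated 6 September 2024 and gives exact cohort sizes, so collection may be over. If it is, state in the SAP which rule sites followed and label the FACE-Q summary accordingly.
2. **SCAR-Q label.** In SAP 10.1 label the mean 'among subjects reporting a scar' and print the no-scar share next to it for each cohort and visit.
3. **One added table.** By cohort and visit, with all full-analysis subjects who answered the scar question as denominator: no scar; scar with all twelve items 'Not at all'; scar with any item above 'Not at all'. No score is imputed. Subjects with a scar but incomplete items need a stated row or rule.

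Items 2 and 3 use data the SAP already plans to report and cost one label and one table. They should go in before database lock, since SAP 5.2 treats later additions as post hoc. Item 1 costs a wording change and, if still feasible, a few more FACE-Q questionnaires.

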# 8.4 Safety Assessments

#### 8.4.1 Physical Examination

Limited physical examinations will include a dermatologic examination, including a Fitzpatrick Skin Type assessment (Screening only). Other systems will be examined as deemed necessary by the investigator depending on clinical signs and symptoms.

Screening Physical examination findings should be recorded on the medical and surgical history eCRF. Post-Screening limited physical examinations will be performed predose at each study visit. Additional physical examinations (limited or complete) may be performed as medically necessary, in the opinion of the investigator, and new findings recorded on the AE eCRF as appropriate.

Physical examinations will be performed at the EOT (excision) visit, 4 - 6 week (Part 1) and 12 to 14 weeks (Part 2) after the subject's first VP-315 treatment.

## 8.4.2 Vital Signs Data

Height and weight will be obtained at Screening and EOS.

Vital signs (e.g., body temperature, BP, and heart rate [HR]) will be obtained at all visits after the subject has been in the supine position for at least 5-minutes. Vital signs will be measured at the final evaluation during the EOS visit before the subject is discharged from the study.

On VP-315 dosing days, blood pressure will be monitored serially (observing for hypotension that meets the definitions as described in Section 10.1): just prior to injection, at 1-, 3-, and 5-minutes after each injection, and then every 5-minutes until 2 hours after the last injection of the day using a manual or automated cuff system (Table 8-1). For subjects in Part 2 – Cohorts 4 and 5 expansion groups, monitoring of BP has been decreased to 1-hour post treatment (an additional hour may be continued at the discretion of the PI).

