#### **8.2** Treatment Period

After completion of screening/baseline assessments (Table 8-1), subjects will be enrolled to receive intratumoral VP-315. In Part 1, each 7-day treatment week comprises up to 3 consecutive treatment days followed by a no-treatment period of at least 4 days. Once a target lesion has necrosed, treatment of that lesion stops, and treatment of subsequent target lesions may continue on Day 1 of the following week. Subjects may be treated for a maximum of 2 treatment weeks. In Part 2 of the study, each 7-day treatment week comprises up to 2 or 3 consecutive treatment days followed by a no-treatment period of at least 4 days.

After each treatment, all subjects in Part 1, Part 2 – Cohort 1, Cohort 2 and Cohorts 4 and 5 (first 10 subjects in each) will remain in the study center for up to 2 hours for safety monitoring (e.g., continuous blood pressure, electrocardiographic and AE monitoring) After each treatment, the additional 20 subjects enrolled into Cohort 4 and 5 expansion groups: will remain in the study center for up to 1-hour (reduced from 2-hours) post second injection for safety monitoring (e.g., continuous blood pressure, electrocardiographic and AE monitoring), an additional hour may be continued at the discretion of the PI. Plasma PK sampling will be collected (in Part 2, Cohorts 4 and 5 expansion groups) as detailed in Table 8-1.

The subject will return to the clinic the day after treatment for assessment by the investigator. The treatment site will be photographed and assessed for CRA (Appendix 1) and PGA of response to treatment (Appendix 2), with images uploaded for real-time assessment by the SRC (Part 1) and/or Medical Monitor (Part 2). The CRA and PGA will be performed by the investigator or trained personnel at each treatment visit, at the EOT visit, and at the EOS visit.

Subjects in Part 2 (Cohorts 4 and 5) with only 1 target lesion, that complete week one of treatment and the W1 safety assessment visit without complete necrosis should return for a Limited Safety Assessment Visit on W2D1 for further evaluation of the lesion for necrosis.

Subjects that complete two weeks of treatment and the W2 safety assessment visit without complete necrosis should return for a Limited Safety Assessment Visit on W3D1.

Nontarget BCC lesions will be observed for abscopal effect.

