### 9.3. Vital Signs Including Height and Weight

Summaries for vital signs will be provided using descriptive statistics and the safety population. Vital signs include the following parameters:

- Blood Pressure, Systolic (mmHg)
- Blood Pressure, Diastolic (mmHg)
- Height (cm)
- Weight (kg)
- BMI (kg/m^2)

- Heart Rate (beats/min)
- Respiratory Rate (breaths/min)
- Temperature (C)

Non-blood pressure vital signs (Height, Weight, BMI, Heart Rate, Respiratory Rate, Temperature) will be presented in one summary and blood pressure (Systolic, Diastolic) will be presented in other summaries (one each for systolic and diastolic).

Summaries will present scheduled visit and include baseline (Screening, Baseline, W1D1, W1D2, W1D3, W1 Safety Assessment, W2D1, W2D2, W2D3, W2 Safety Assessment, Limited Safety Assessment, EOT, EOS 1 Week Post-excision, EOS 2 Weeks Post-excision – not all vital signs are collected at all scheduled visits) within the parameters mentioned previously in this section of the SAP and include descriptive statistics for baseline and change from baseline for post-baseline visits, if possible.

Blood pressure is also to be measured and will be displayed by scheduled timepoint (Pre-injection, 1 Minute Post-injection, 3 Minutes Post-injection, and then 5 through 120 Minutes Post-injection in increments of 5 minutes) within injection (Injection 1, Injection 2 – not all timepoints are collected for all injections) within scheduled visit and include descriptive statistics for change from pre-injection for post-injection readings on that same visit, if possible.

A summary will also be provided for the number of events, and the number and percentage of subjects with at least one event, for each of the following parameters within injection visit (W1D1, W1D2, W1D3, W2D1, W2D2, W2D3):

- 20 mmHg decrease in systolic BP with absolute systolic BP < 100 mmHg
- 20 mmHg decrease in systolic BP with clinical symptoms
- Absolute diastolic BP < 60 mmHg

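### SAP 9.3 counts hypotension events over a 2-hour window in some groups and a 1-hour window in others, with no common cut-off, so expansion rates and the pooled total can be lower from shorter observation alone

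*Protocol*

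**What the plan says.** **Monitoring.** On dosing days Protocol 8.4.2 schedules readings just before injection, at 1, 3 and 5 minutes after each injection, "and then every 5-minutes until 2 hours after the last injection of the day using a manual or automated cuff system". For the Cohort 4 and 5 expansion groups the same section states that "monitoring of BP has been decreased to 1-hour post treatment" and adds that "an additional hour may be continued at the discretion of the PI". Protocol 8.2 places Part 1, Cohorts 1 and 2, and the first ten subjects of each of Cohorts 4 and 5 on the 2-hour stay.

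**Tabulation.** SAP 9.3 lists a single set of timepoints for all groups: pre-injection, 1 and 3 minutes, "and then 5 through 120 Minutes Post-injection in increments of 5 minutes". It notes that "not all timepoints are collected for all injections". For the hypotension criteria it then plans: "A summary will also be provided for the number of events, and the number and percentage of subjects with at least one event", by injection visit. One criterion is "Absolute diastolic BP < 60 mmHg". Falls in systolic pressure are assessed against three references, one of which is the preceding reading on the same visit. The section gives no cut-off time, no denominator for time observed and no rule for the optional extra hour.

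**Groups.** SAP 5.5 shows the initial and expansion parts of Cohorts 4 and 5 in separate columns and adds an overall Part 2 column. SAP 9.3 does not restrict these. SAP 14, which lists departures from the protocol, does not mention the unequal windows.

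**The concern.** A count of subjects with at least one qualifying reading depends on how long, and how often, they are measured. Diastolic pressure below 60 mmHg needs only one reading and no fall from a reference value. Protocol 5.3 admits subjects with diastolic pressure from 70 mmHg upwards, so ordinary variation could produce such a reading at any time during monitoring. The reading-to-reading systolic rule makes each extra reading a further chance to qualify. The table also reports a number of events. SAP 9.3 does not say whether each qualifying reading is a separate event; if it is, that count depends directly on the number of readings.

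At equal underlying risk, the expansion groups can therefore show the same rate as the initial groups or a lower one, never a higher one apart from chance. A reader who sets the columns side by side, or uses the pooled rate, could take a shorter window for better tolerability. This matters because Part 2 is meant to inform a pivotal design, and hypotension is one of the reactions singled out as a TRAE SI.

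The optional hour complicates matters. If investigators extend monitoring in subjects who look unwell, the length of observation depends on the outcome.

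**Working it through.** The documents state no hypotension rate, onset distribution or power calculation, so there is no planned figure to reproduce. The only total that can be checked is the Part 2 sample size.

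**Step 1. Who has which window (SAP 3.2 to 3.7).**
- Cohort sizes: 6 + 3 + 36 + 37 = 82, which agrees with the stated Part 2 N.
- Two-hour schedule: 6 + 3 + 10 + 10 = 29.
- One-hour schedule: 26 + 27 = 53.
- Within Cohorts 4 and 5 alone: 20 against 53, of 73.

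**Step 2. Scheduled readings after the last injection.** Three early readings (1, 3 and 5 minutes), then one every 5 minutes from 10 minutes.
- To 120 minutes: 3 + 23 = 26.
- To 60 minutes: 3 + 11 = 14.
- Ratio 26/14 = 1.86.

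**Step 3. Scheduled post-injection readings over a split-dose day.** The two injections are 15 to 30 minutes apart, and readings follow each.
- 15-minute gap (1, 3, 5, 10, 15): 5 more, so 31 against 19, ratio 1.63.
- 30-minute gap: 8 more, so 34 against 22, ratio 1.55.

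**Step 4. Illustration with equal risk at every reading (assumed).** Suppose each reading qualifies independently with probability q. Then P(at least one per visit) = 1 − (1 − q)^k, with k = 31 or 19. The pooled value for Cohorts 4 and 5 is (20 × two-hour rate + 53 × one-hour rate)/73.

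| Assumed q | Two-hour | One-hour | Pooled, Cohorts 4 and 5 | Ratio |
|---|---|---|---|---|
| 0.2% | 6.0% | 3.7% | 4.4% | 1.61 |
| 0.5% | 14.4% | 9.1% | 10.5% | 1.58 |
| 1% | 26.8% | 17.4% | 20.0% | 1.54 |
| 2% | 46.5% | 31.9% | 35.9% | 1.46 |

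This is a high-side illustration. Readings 5 minutes apart in one person are likely to be correlated, which narrows the subject-level gap. If every qualifying reading counts as an event, the expected number of events is k × q. Its ratio then stays at 31/19 = 1.63 even with correlated readings, provided q is constant.

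**Step 5. Illustration by share of late first events (assumed).** Let R be the two-hour rate and f the share of subjects with an event whose first one comes after 60 minutes. The one-hour rate is R(1 − f), and the Part 2 Total is [29R + 53R(1 − f)]/82. With R = 20% in every group:

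| Assumed f | Two-hour | One-hour | Part 2 Total |
|---|---|---|---|
| 0 | 20% | 20% | 20% |
| 10% | 20% | 18% | 18.7% |
| 25% | 20% | 15% | 16.8% |
| 50% | 20% | 10% | 13.5% |

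Both illustrations assume that no expansion subject has the optional hour. Any extension moves the one-hour figures towards the two-hour figures.

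**The case against.** The strongest reply is that the effect may be nil. Protocol 2.2.2 describes the blood pressure effect in animals as transient, and Protocol 2.3.1 reports that Day 1 events in an earlier study lasted minutes. If every first qualifying reading falls within the hour, subject-level rates are unaffected. This stands as a lower bound. It does not settle the matter: the earlier-study remark concerns doses below 4.0 mg, no onset times are given for 8 mg, and the diastolic criterion in the SAP table does not require that the reading be caused by the drug.

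A second reply is that the plan already separates the groups, displays pressure by timepoint and lists reading times, in a study without inference. It is true that only the totals are mixed, and that the Part 2 Total already combines different regimens. The separate columns of the event table still set unequal windows beside one another without warning.

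A reader might go further and infer that the TRAE SI totals mix two definitions, and that they too should be cut at 60 minutes. The documents do not support this. TRAE SIs are adverse events recorded in the database (SAP 4.1) and are counted on any treatment day in every Part 2 group (SAP 9.1 and 14). The definition is common; what differs is the chance of detecting a symptom-free, pressure-defined event once the cuff is off. A cut would remove real events from a primary safety endpoint.

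**Conclusion.** The point holds as a tabulation defect in SAP 9.3. Scheduled windows differ, the event table has no common cut-off, and the Part 2 Total combines 29 two-hour with 53 one-hour subjects. At equal risk the resulting artefact runs in one direction, towards lower expansion rates.

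Its size cannot be determined from the documents. At subject level it runs from zero, if all first events fall within 60 minutes, to about a 1.5- to 1.6-fold ratio, if risk is the same at every reading and readings are independent.

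Two stronger inferences are tempting and should be resisted. One is that the rates must differ because of observation time: they can differ, but only if qualifying readings occur after the first hour. The other is that two-hour subjects have about twice as many readings per dosing day: 26 against 14 applies only after the last injection, and the whole-day ratio with split dosing is 1.55 to 1.63. Nor is the expansion window fixed at one hour; it is one to two hours, varying by subject.

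This is a cheap improvement to a descriptive safety table. It implies nothing about how long subjects ought to be monitored.

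**What to change.** In the hypotension event table of SAP 9.3:

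1. Count events, and subjects with at least one, up to 60 minutes after the last injection of the day in all groups. Use this count for the pooled totals and for any comparison of initial with expansion groups.
2. Show events at 61–120 minutes in a separate row, with the number of subjects monitored that long. Include expansion subjects whose monitoring the investigator extended, and identify them as such.
3. State whether each qualifying reading is a separate event.
4. Footnote the scheduled windows by group.

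Leave the TRAE SI counts on the treatment-day rule, and add a footnote that pressure-defined events had unequal detection windows. List the change in SAP 14.

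The cost is one extra row per parameter and a time filter on readings whose time, timepoint and injection number are already planned for the SAP 9.3 listing. For the row that requires symptoms, the filter applies to the pressure reading; symptoms would still be matched by date, as planned. No data are lost, but late events no longer appear in the headline count of this table.
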